11.0 Specimen Collection and Banking (if applicable)

Not applicable.

12.0 Data Management

All documentation and data concerning each participant will be coded to protect confidentiality. All data collection and storage processes and locations will use study equipment (i.e., heart rate variability monitors, computers, College of Health Professions DA server) that is password protected, encrypted, and behind the MUSC firewall. All study related equipment will be locked in the office of the PI when not in use. There will be no transfer of data to a third party.

13.0 Provisions to Monitor the Data to Ensure the Safety of Subjects (if applicable)

All documentation and data concerning each participant will be coded to protect confidentiality. All data collection and storage processes and locations will use study equipment (i.e., heart rate variability monitors, computers, College of Health professions DA server) that is password protected, encrypted, and behind the MUSC firewall. All study related equipment will be locked in the office of the PI when not in use. There will be no transfer of data to a third party.

Children undergoing HCT will experience symptoms related to the HCT and may experience additional medical complications. Our study involving art and physical therapy interventions will only be carried out during the in-patient phase, which will be helpful when considering adverse effects because a variety of

healthcare professionals will be at hand to possibly prevent and ameliorate any adverse events. For example, prior to each daily session, the art and/or physical therapist will ask the child's nurse if the patient is medical stable to participate. If the nurse, reports that the child is not medically stable, then the child's session will be postponed until stable.

Common symptoms following transplant include fatigue and deconditioning which is associated with lower strength and endurance. We believe children' participation in this study will lead to temporary reports of elevations in fatigue, weakness, and poorer endurance symptoms; however, we will not view these as adverse events since these symptoms are also common to increases in activity level that will be generated by art and physical therapy.

Unanticipated adverse events that might be possible are falls secondary to possibly osteostatic hypotension or clumsiness. If an unanticipated event were to occur, the intervention therapists would immediately report the incident to the child's nurse and attending physician so that appropriate assessment and treatment can begin. The intervention therapist would then report the event to the PI, who would contact the IRB and complete an adverse event report. To avoid experiencing an adverse event, before each intervention session, study team members will communicate with each child's nurse concerning child's medical status that day. If nursing agrees the child's statue is stable, the intervention will proceed. If nursing reports that the child's status is not stable, the intervention will be postponed. If the child experiences a change in medical status that requires transferred to a more complicated medical environment, such as the ICU, study intervention will be postponed until return to the HCT unit. If a child's medical status improves and they are transferred to a "regular" hospital room, the study intervention will continue. Once the child is discharge to home, the study intervention will be stopped even if 10 days of the study intervention have not been provided.

We consider this study to be low risk however our data and safety monitoring plan will be continuous, close monitoring by the study investigator/co-investigators of all participants. The PI ([name]) and Co-I's ([name]) will meet once a month discuss data and safety monitoring. During these meetings we will look for any negative trends in the data we have collected (Self Assessment Manikin, PEDI, 6-Minute Walk Test, heart rate variability, accelerometry) that could indicate adverse events and provide a timely summary report of adverse events to the IRB.

Any reportable safety events that are unexpected, serious or may be related to the subjects' participation in this research will be reported to the MUSC IRB and NEA in accordance with their policies.

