15.0 Risks to Subjects

As with any study there is a risk of loss in confidentiality. All documentation and data concerning each participant will be coded to protect confidentiality. All data collection, storage processes, and storage locations will use study specific equipment (i.e., heart rate variability monitors, computers, College of Health professions DA server) that is password protected, encrypted, and behind the MUSC firewall.

Secondary to undergoing HCT, children often experience sympathetic dominance/physiological and emotional distress (increased heart rate, decreased HR variability, fear) and physical deconditioning (fatigue, atrophy, weakness, decreased endurance) in the short and long term. This study seeks to ameliorate these symptoms by providing AT and PT; however, during AT and PT, children may experience an increase in these symptoms in the short term. Since this study is being carried out during an

in-patient phase of treatment, the HCT care and study team will be able to easily monitor and manage any adverse events.

Unanticipated adverse events that might be possible are falls secondary to possibly orthostatic hypotension or clumsiness during physical therapy and/or all walking type activities.

The treatment you receive may prove to be less effective or to have more side effects than the other study treatment(s) or other available treatments.

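### Section 13.0 keeps expected fatigue, weakness and reduced endurance out of the adverse events with no defined limit, so non-serious symptoms that stop or prevent a session need not be counted as harm in either arm

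*Combined protocol and SAP*

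**What the plan says.** Section 13.0 opens the matter with the clinical background: "Common symptoms following transplant include fatigue and deconditioning which is associated with lower strength and endurance". It then predicts that "participation in this study will lead to temporary reports of elevations in fatigue, weakness, and poorer endurance symptoms", and states the exclusion: "we will not view these as adverse events since these symptoms are also common to increases in activity level that will be generated" by art therapy (AT) and physical therapy (PT). Section 15.0 lists the same kind of symptom as a risk: "during AT and PT, children may experience an increase in these symptoms in the short term".

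The safety provisions around this, all in Section 13.0, are:

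- **Nurse check before each session.** "If the nurse, reports that the child is not medically stable", the session is put off until the child is stable.
- **Adverse event report.** "If an unanticipated event were to occur, the intervention therapists would immediately report the incident" to the nurse and attending physician, and then to the principal investigator, who contacts the IRB and completes the report. Falls are the example given.
- **Investigator monitoring.** The investigators undertake ongoing close monitoring of all participants and meet monthly to look for "negative trends in the data we have collected (Self Assessment Manikin, PEDI, 6-Minute Walk Test, heart rate variability, accelerometry) that could indicate adverse events".
- **External reporting.** "Any reportable safety events that are unexpected, serious or may be related" to participation go to the IRB and the NEA under those bodies' policies.

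Section 9.0 adds declined days to the end of the treatment period and withdraws a child who declines three days running. Section 14.0, on withdrawal, is marked not applicable.

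**The concern.** The plan names an effect that it expects its own intervention to cause and decides in advance not to count it. For mild tiredness after exercise in a child recovering from transplant, that is sensible, because otherwise every session would generate an entry. The difficulty is the boundary. 'Temporary' could mean an hour, a night or several days. Nothing separates tiredness that a child works through from tiredness that ends the session or leads the child to refuse the next one.

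The experimental arm puts 45 minutes of AT directly before 30 minutes of PT, starting at about Day 15 of the transplant. Whether children can complete that sequence is a practical question for anyone planning the larger trial mentioned in Section 10.0. Under the exclusion as written, the trial could finish without a count, by arm, of sessions stopped or missed because of these symptoms.

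**Working it through.** The point turns on a definition, so the check is a reading of the provisions against one case. No alpha, power or effect size enters. Take a child in either arm who becomes too tired to finish PT, or too tired to attend the next day, without the event being serious.

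1. **Is it an adverse event by definition?** Section 13.0 excludes temporary fatigue, weakness and reduced endurance. The child recovers, so 'temporary' can be met. No duration, grade or functional criterion brings the episode back in. Section 15.0 adds only that the increase is short term, which is equally open.
2. **Does the adverse event report catch it?** The trigger is an unanticipated event. Section 13.0 has already predicted these symptoms, so on an ordinary reading the trigger is not met.
3. **Does the IRB and NEA clause catch it?** Possibly. Fatigue after therapy may well be related to participation. But the clause covers reportable events under policies that are not in the documents, and it follows a statement that these symptoms are not adverse events. The two sentences pull in different directions.
4. **Does the nurse check catch it?** It may postpone a session. Nothing requires the reason to be kept, and it does not address a session that starts and is then cut short.
5. **Does investigator monitoring catch it?** Close monitoring might bring it to notice. The monthly review names five sources: the Self-Assessment Manikin, PEDI-CAT, 6-Minute Walk Test, heart rate variability and accelerometry. None records why a session stopped or was missed, and no trigger is stated. Less walking on the accelerometer shows that the child did less, not why.
6. **Do the missed-day rules catch it?** Section 9.0 needs a count of declined days to operate, but does not ask for the reason. The post-test in Section 10.0 is set for the day after the tenth intervention day, so a child withdrawn after three refusals has no scheduled post-test.

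No step requires the episode to be recorded as harm, or its reason to be kept. The wording is the same for both arms.

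Scale of the planned treatment (Sections 3.0 and 6.0):

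- PT: 30 minutes x 10 sessions = 300 minutes per child in each arm.
- AT: 45 minutes x 10 sessions = 450 minutes per child, combined arm only.
- Sessions: 20 children x 10 = 200.

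The documents give no rate for session-limiting fatigue, so the number of episodes that could go uncounted cannot be estimated from them.

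**The case against.** The strongest reply is that the exclusion is narrower than it looks. It covers passing elevations of symptoms that normal activity produces. A child who cannot finish a session has arguably gone beyond that rationale, so the episode could be treated as unanticipated. The clause on events possibly related to participation is a second open route, and close monitoring of all participants is promised. Much of the count may also be recoverable: declined days have to be tallied, the coordinator monitors all sessions for adherence to procedures (Section 3.0), and the heart rate and accelerometer files should leave traces of missed or shortened sessions. What lacks a stated home is the reason, and a short academic protocol need not show every form field.

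Much of this stands. It limits the claim to 'need not be counted'; the plan does not prohibit recording. It does not remove the gap, because each route depends on a reader choosing the more generous of two interpretations, and none requires the reason to be kept.

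The reply is also right that tolerability is not an aim and that Section 10.0 uses the term pilot data only for Aim 1.

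A reader might infer more than the text supports:

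- **That serious exhaustion would go unreported.** The IRB and NEA clause expressly covers serious reportable events.
- **That the exclusion hides a harm specific to the combined arm, since daily therapy is 75 minutes against 30.** PT time is equal, and scheduled AT time is not a measure of exertion. Nothing shows fatigue to be the harm most likely to differ; Section 2.0 ties gouache without a brush to high anxiety, which is a different harm.

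**Conclusion.** The concern holds in a limited form and carries minor weight. Section 13.0 sets an explicit exclusion bounded only by an undefined word, and links the adverse event report to unanticipated events. Followed as written, the plan can leave non-serious fatigue, weakness or reduced endurance that stops or prevents a session uncounted as harm in either arm. No aim's estimate or test is altered; the loss is in the safety and tolerability description.

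This rests on reading 'unanticipated' in its ordinary sense, and on the provisions in the documents alone. The IRB and NEA policies are not among them, and if those policies make such episodes reportable, the gap in external reporting narrows. The absence of a recorded reason would remain unless a data form outside the documents already collects it.

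**What to change.** In Section 13.0, limit the exclusion to symptoms that have resolved by the next scheduled session and did not affect participation. Record fatigue, weakness or reduced endurance as a non-serious adverse event if it does any of the following:

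- stops a session early;
- causes the next session to be refused or postponed;
- prompts a request for medical assessment.

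Events that meet the existing serious or external reporting rules stay under those rules.

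Keep a one-line session log in both arms: completed, stopped early or missed, with a reason (fatigue, weakness or endurance; distress or anxiety; medical instability; other). Show it by arm at the monthly meeting and report it descriptively at the end, with no test. Leave the nurse check, the IRB and NEA clause and the trend review as they are.

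**Cost.** A short amendment and at least 200 log lines if every child completes ten sessions. Missed and made-up sessions add lines; early discharge or withdrawal removes some. At an assumed 1 to 2 minutes a line, 200 lines take 200 to 400 minutes, or 3.3 to 6.7 hours over the trial. No extra staff or procedure is needed, though the coordinator's present task is to monitor procedures, not symptoms.

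**Downsides.** Some entries will reflect the transplant and not the sessions. Therapists know the arm, so attribution is unblinded. A child's course, at about Day 15 to 24, can fall between two monthly meetings, so the log helps later children and the final report more than the child concerned.

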14.0 Withdrawal of Subjects (if applicable)

Not applicable.

15.0 Risks to Subjects

As with any study there is a risk of loss in confidentiality. All documentation and data concerning each participant will be coded to protect confidentiality. All data collection, storage processes, and storage locations will use study specific equipment (i.e., heart rate variability monitors, computers, College of Health professions DA server) that is password protected, encrypted, and behind the MUSC firewall.

Secondary to undergoing HCT, children often experience sympathetic dominance/physiological and emotional distress (increased heart rate, decreased HR variability, fear) and physical deconditioning (fatigue, atrophy, weakness, decreased endurance) in the short and long term. This study seeks to ameliorate these symptoms by providing AT and PT; however, during AT and PT, children may experience an increase in these symptoms in the short term. Since this study is being carried out during an

in-patient phase of treatment, the HCT care and study team will be able to easily monitor and manage any adverse events.

Unanticipated adverse events that might be possible are falls secondary to possibly orthostatic hypotension or clumsiness during physical therapy and/or all walking type activities.

The treatment you receive may prove to be less effective or to have more side effects than the other study treatment(s) or other available treatments.

16.0 Potential Benefits to Subjects or Others

Potential benefits to children in the study may include reduced and/or improved sympathetic dominance/ physiological and/or emotional distress and reduced and/or improved physical deconditioning in the short and long-term as a consequence of HCT. If daily AT and PT during the in-patient stay of improves outcomes, the support for daily AT and PT over the course of HCT may be improved.

17.0 Sharing of Results with Subjects

Results will be publicly disseminated through peer-review processes, which will be available to participating families and all interested others through the NEA website and other journals.

